## **10.6. Efficacy**

Due to the small size of this pilot, proof-of-concept trial, interim analyses for efficacy would not be appropriate.

We will recruit and screen up to 48 participants to obtain 12 participants with evaluable data to study and compare pre-VOR/HXT and post-VOR/HXT frequency of HIV infection per million resting CD4+T cells, and will analyze using a non-parametric 2-sided sign test to determine whether or not a significant decrease of IUPM is observed, as below in section 10.7.

## **10.7. Analysis**

### **10.7.1. Primary Analysis**

For the safety endpoint, we will record and describe all study treatment-related adverse events through the end of study.

Ultimately, we aim to detect a significant depletion of the latent reservoir, by measuring the frequency of resting cell infection using the QVOA. We will analyze pre-VOR/HXT and post-VOR/HXT frequency of HIV infection per million resting CD4+T cells using a non-parametric 2-sided sign test (and the Wilcoxon signed rank test if no assay censoring) to determine whether or not a significant decrease of IUPM is observed. With 12 participants there is 80% power to reject H0 (change expected with ART alone) in favor of HA (greater change than expected with ART) if

the true probability of observing a decrease in IUPM in a participant after VOR/HXTC is 0.93.

In addition to summarizing the number and proportion of participants who show decrease in IUPM after VOR/HXTC, we will describe the magnitude of the changes in decrease in IUPM after VOR/HXTC via the median fold-change and corresponding 95% confidence interval. We will also summarize the proportion of participants with >6-fold decreases; this magnitude change is rarely seen in participants on stable ART [64]. We will therefore consider a >6 fold change from baseline to post VOR-HXTC treatment as significant on an individual participant basis. For n=12 participants, precision calculations are analogous to those for safety endpoints. In particular, if all 12 participants have a >6 fold change from baseline, then the exact 95% confidence interval (CI) for the probability of significant depletion of the latent reservoir would be [0.74, 1.00], i.e., one could confidently rule out depletion probabilities less than 74%. If 11 of 12 participants achieve significant depletion, the 95% CI would be [0.62, 1.00]. Other possible observed proportions and 95% CIs are given in Table 5.

For the first 6 participants who had HIV RNA expression per million resting CD4+T cells measured after VOR exposure (ex vivo exposure to VOR in the screening step; in vivo exposure to first VOR dose), as a gateway to advance through the study protocol, we will assess within-participant RNA changes. We will analyze using the non-parametric 2-sided Wilcoxon rank sum test to determine whether or not a significant increase of RNA expression is observed in these participants comparing RNA levels measured in each of 24-36 replicate pools of 1 million resting CD4+ cells. Pools with undetectable RNA will be considered as 0 copies and analyzed as the lowest rank in this rank-based statistical test.

For the first 6 participants, the pre-VOR RNA expression will be determined as the median RNA copies over the individual pools of one million participant cells tested prior to VOR (setting undetectable RNA pools as 0 copies), and the post-VOR RNA expression level will be similarly determined. Changes in RNA expression will be evaluated by the sign test and the proportion of participants with increases versus decreases. Summaries of the magnitude of changes will be examined in terms of median fold-changes.

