**7.4. Screening Failure and Re-screening Procedures**

Participants unable to meet laboratory values as defined in the protocol and defined inclusion/exclusion criteria may repeat the disqualifying lab/s once to meet eligibility prior to enrolling at Visit 2.

Participants unable to meet protocol defined eligibility criteria at the Screening Visit after repeating disqualifying labs per protocol, can re-screen again at the Principal

Investigator's (or designee) discretion. In such cases, the participant keeps the same PID.

**7.4.1. Failure of the frequency of resting CD4+ T cell infection to be  $\geq 0.3$  infected cells per million as determined by QVOA assay at baseline evaluation.**

If a participant fails to have a frequency of resting CD4+ T cell infection to be  $\geq 0.3$  infected cells per million as determined by QVOA assay at the baseline leukapheresis in Step 1, study participation is terminated. The SID for this participant will be retired and will not be used again. These participants will be replaced in the study.

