Include all current medications and any PRN medications used within the past 30 days.

- All medication taken within 30 days of study screening.
- After study entry, record only new and discontinued over-the-counter, herbal, dietary and vitamin supplements, and prescription medications.
- Document all doses of VOR and HXTC therapy and permanent discontinuation.

8.1.1.14. **Signs, Symptoms, and Diagnosis of Illnesses and Diseases**

At screening, all signs and symptoms, regardless of grade, that occurred within the 30 days before entry must be recorded. After study entry, record any new diagnosis or illnesses that develop.

After study entry, grade  $\geq 3$  signs and symptoms must be recorded. Record only signs and symptoms that are related to VOR or HXTC therapy and all signs and symptoms that lead to a change in treatment, regardless of grade.

8.1.1.15. **Blood collection**

Please reference SOE in Appendix A

8.1.1.16. **Urine Collection**

Please reference SOE in Appendix A

8.1.1.17. **Assessment of adverse events**

Please reference protocol section 9.1

8.1.1.18. **Leukapheresis**

Participants will undergo two Leukapheresis procedures. The baseline leukapheresis will be completed at or after Visit 2. Participants will advance to Step 3 based on an IUPM measurement  $\geq 0.3$ . The 2nd leukapheresis will take place at the End of Study Intervention visit in Step 6, Visit 23.

All protocol required leukapheresis products will be transported on the day of collection to the [name] Laboratory on the UNC campus.

All leukapheresis procedures will occur at the UNC Apheresis Lab located in the UNC Blood Bank or at a local contracted blood collection center.

Note: Refer to the UNC Apheresis SOP and Study Specific Lab Manual for procedures specific to this study.

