## **10. STATISTICAL CONSIDERATIONS**

### **10.1. General Design**

This is a phase I, single-site study to evaluate the effects of VOR and HXTC therapy on persistent HIV-1 Infection in HIV-infected individuals suppressed on ART. Twelve participants with durable viral suppression will be enrolled and will complete the study. All participants will receive the same treatment and if eligible, will be dosed with VOR and receive HXTC infusions. Participants will continue their baseline ART regimen throughout the study.

If the baseline IUPM  $\geq 0.3$ , participants will have a blood sample sent to CNH for production of HXTCs. Upon release of HXTC, participants will be clinically assessed to complete the two treatment series with oral VOR 400 mg doses combined with HXTC infusions over a 3 month period. VOR will be administered every 72 hours and each treatment series will consist of 10 doses of VOR 400 mg.

In Step 4 (Series 1), participants will receive two HXTC infusions along with 10 doses of VOR 400 mg. The HXTC infusions will be administered 6 hours after the 1st and 6th VOR doses.

In Step 5 (Series 2), participants will receive three infusions along with 10 doses of VOR 400 mg. The first two infusions will be administered 6 hours after the 11th and 16th doses of VOR. The 5th and final HXTC infusion will occur 1 – 3 days after the 20th VOR dose.

The 2nd and final leukapheresis will occur at least 4 weeks after the last HXTC infusion.

Resting cell infection frequency will be determined pre VOR-HXTC dosing with the baseline leukapheresis and post VOR-HXTC dosing with 2nd leukapheresis.

Longitudinal follow-up to measure the effectiveness of the intervention will continue for 9 weeks after the last HXTc infusion. Serial blood draws will be obtained pre and post-VOR-HXTc dosing throughout the study to monitor immune response.

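### Section 10.7.1 words its null as the change expected on ART alone but sets no null probability, alpha or rejection count; a default test would test no change, on a baseline already selected at IUPM ≥0.3

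*Combined protocol and SAP*

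**What the plan says.** Section 10.7.1 compares IUPM before and after treatment and names the test and its purpose: "non-parametric 2-sided sign test (and the Wilcoxon signed rank test if no assay censoring) to determine whether or not a significant decrease of IUPM". Section 10.6 announces the same sign test. Section 10.7.1 describes H0 as the "change expected with ART alone" and HA as a greater change than that. It then states: "With 12 participants there is 80% power to reject" H0 if "the true probability of observing a decrease in IUPM in a participant after VOR/HXTC is 0.93". No p0, alpha or rejection count is given. Two-sided 0.05 appears only in section 10.7.2, for the additional secondary endpoints.

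On the baseline, section 10.1 says: "Resting cell infection frequency will be determined pre VOR-HXTC dosing with the baseline leukapheresis". Section 8.1.1.18 says: "Participants will advance to Step 3 based on an IUPM measurement" of at least 0.3, and provides for two leukaphereses in all, one before and one after treatment. Under section 7.4.1, if the baseline value is below 0.3, "study participation is terminated" and the participant is replaced. The note in section 4.1 lets people with an IUPM of at least 0.3 in earlier UNC studies move to Step 3 before the new baseline result is known. All participants receive the same treatment (10.1).

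**The concern.** Two things push the same way. First, the baseline is a single noisy assay result truncated from below. Among people who pass the gate, readings that are high by chance are over-represented, so a second reading tends to be lower even if nothing has changed. Second, time passes on ART between the two readings. From the visit windows this is 4–6 weeks to Visit 5, 4–10 weeks to Visit 6, up to 3 weeks to Visit 7, and 16 weeks to Visit 23: about 24–35 weeks for participants whose product is made in the trial. Any fall on ART alone adds to the first effect.

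The wording of H0 recognises the second effect, but nothing in the plan puts it into the test. An analyst who runs a standard paired sign test or signed-rank test will test no change. The rejection count is also open, so whether 10 decreases in 12 counts as significant could be settled after the data are seen. At stake is a claim of reservoir depletion in a trial without an ART-alone comparison.

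**Working it through.** **1. The plan's own power figure.** With X the number of decreases in n = 12, P(X ≥ k | p) = Σ C(12, j) p^j (1−p)^(12−j) over j ≥ k. Two-sided 0.05 is assumed, because alpha is not stated for this test.

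Null side, p0 = 0.5:
- k = 9: 299/4096 = 0.073, two-sided 0.146, not significant
- k = 10: 79/4096 = 0.0193, two-sided 0.0386, significant
- k = 11: 13/4096 = 0.0032, two-sided 0.0063

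Power at 0.93: 0.93^12 = 0.4186; 12 × 0.93^11 × 0.07 = 0.3781; 66 × 0.93^10 × 0.07² = 0.1565.
- ≥12/12: 41.9%
- ≥11/12: 79.7%
- ≥10/12: 95.3%

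The stated 80% is therefore reproduced by ≥11/12, not by the default rule ≥10/12.

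**2. Which p0 gives ≥11/12.** With an upper tail of at most 0.025, ≥10/12 stops being allowed above p0 = 0.516, and ≥11/12 stops being allowed above p0 = 0.615. So ≥11/12 follows from p0 between about 0.52 and 0.615 at two-sided 0.05. It also follows from p0 = 0.5 at two-sided 0.01 (0.0063 ≤ 0.01 < 0.0386). The text does not say which was meant.

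**3. Size of the gating effect.** The documents give no assay SD, population distribution or gate pass rate, so these are assumptions:
- Assay SD per reading: section 10.7.1 calls a >6-fold change rare on stable ART. Reading that as 1.96 SD of a difference gives log10(6)/1.96/√2 = 0.28 log10.
- Between-person SD: 0.4 to 0.6 log10. Population median: 0.3 to 2.0 IUPM.
- Pre = truth + error; post = truth − fall + error; keep pre ≥ log10(0.3).

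The simulated P(decrease) goes into the binomial tail. The signed-rank test is simulated in sets of 12, rejecting at a rank sum ≥65 (upper tail 2.1% under symmetry). Ranges are over the two between-person SDs. The entries are false-positive rates toward a decrease.

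| Median IUPM | Pass gate | P(decrease), no true change | ≥10/12 | Signed-rank | ≥11/12 |
|---|---|---|---|---|---|
| 0.3 | 50% | 0.60–0.63 | 8.0–12.5% | 10–16% | 1.9–3.3% |
| 0.5 | 63–68% | 0.57–0.59 | 5.8–7.1% | 7–9% | 1.2–1.6% |
| 1.0 | 79–86% | 0.54 | 3.8–3.9% | 4.5–4.6% | 0.7–0.8% |
| 2.0 | 89–95% | 0.52–0.53 | 2.5–2.9% | 2.9–3.4% | 0.4–0.5% |
| p0 = 0.5 (no gate) | – | 0.50 | 1.9% | 2.1% | 0.3% |

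Adding an assumed ART-alone fall of 0.05 log10 (11%) gives, from median 2.0 up to median 0.3, about 5–21% at ≥10/12, 7–29% for the signed-rank test and 1–7% at ≥11/12.

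**4. Wider assumptions.** With assay SD 0.24–0.34, between-person SD 0.3–0.7, 50–90% passing the gate and no true change, the range is 2.6–20% at ≥10/12 and 0.5–6.3% at ≥11/12. With a baseline taken separately from the gating value, P(decrease) returns to 0.50 and the ≥10/12 rate to 1.9%.

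**The case against.** A reader might infer that the plan's test is a test of no change, with a badly inflated error rate. The documents do not support that. Section 10.7.1 words H0 as the ART-alone change, and its power figure fits ≥11/12, which is what a p0 somewhat above 0.5 would give. Under that rule gating alone mostly stays within 2.5%. Even at ≥10/12 the excess is small when the population median is well above the gate: at P(decrease) of 0.52 and 0.54, total two-sided rejection is 4.0% and 4.6%. The larger figures need a low median, an assumed ART-alone fall, or both.

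Nor is the null value the only safeguard. The plan treats a >6-fold change as individually significant because it is rare on stable ART, and it reports the median fold-change with a confidence interval. All participants must have had at least 24 months of ART (5.1.4), which weakens any appeal to rapid decline in those treated from acute infection. Those with stored product skip Visits 5 and 6 (4.3), so the 24–35 week interval is not universal. The section 4.1 route means the gating value is not the baseline for everyone. The trial is a phase I pilot, and section 3.2 lists QVOA as a secondary outcome, although sections 3.1.1.2 and 10.2.1.2 make it primary.

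These points limit the size and severity. They do not supply the missing p0, alpha and count. The >6-fold proportion is only summarised, not tested. An implied ≥11/12 rule also gives no protection to the signed-rank test, which has no offset for ART-alone change.

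**Conclusion.** The point holds as a gap between the stated H0 and the test as specified, made worse by using one QVOA value as both gate and baseline. The direction of the bias is certain: toward declaring a decrease. Its size is not, because it rests on assay variance, population spread, median and ART-alone decline, none of which the documents give. The exposure lies mainly with a default ≥10/12 sign test (about 2.5–12.5% from gating alone) and the signed-rank test (about 3–16%). At ≥11/12 it is modest (0.4–3.3%), rising to about 1–7% only with the assumed 0.05 log10 fall. The power statement and the default test disagree, and the text does not resolve which rule applies. This should be fixed before analysis, but it does not show that an observed decrease would be spurious.

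**What to change.** In section 10.7.1, before analysis:

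- State p0 above 0.5, alpha and the rejection count. For example, ≥11/12 keeps the upper tail at or below 2.5% for p0 up to about 0.615 and delivers the stated 80% power. If available, take p0 from repeat QVOA pairs on stable ART with a first value of at least 0.3 and similar spacing. The citation for the 6-fold threshold needs checking first: entry 64, by its title, concerns a vorinostat-induced cell-death pathway.
- Report exact p-values at p0 = 0.50, 0.55, 0.60 and 0.65 as a sensitivity analysis, not as a condition for the claim. At 0.65, 11/12 has an upper tail of 4.2%, so 12/12 would be required and power at 0.93 would drop to 42%.
- Make the zero-null signed-rank test supportive only, or give it an offset for ART-alone change.
- Show separately the change from the first to the second leukapheresis for participants who entered on an earlier UNC IUPM, whose baseline depends less on the gate. Reconcile the section 4.1 note with section 7.4.1 on whether a new baseline below 0.3 removes them.

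The cost is wording and a small analysis, with no new participants or samples. The downside is a higher bar than the default: power at 0.93 is 79.7% rather than 95.3%, which is what the plan already states.

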#### 3.2.2. Secondary

The secondary outcome will be the impact of VOR and HXTC therapy on the HIV-specific immune response and on the frequency of latent HIV infection, as measured by a QVOA and plasma HIV-1 RNA viremia measured by SCA, an assay with a limit of quantitation of 1 copy/mL.

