#### 10.7.2. Secondary Analysis

The virologic analysis will include comparison of the SCA levels pre-treatment (screening and entry) compared to post-treatment in Steps 5 and 6. We assume that the probability would be 0.10 (10%) for a baseline (pre-entry, entry) detectable SCA  $\geq 1$  copy and the probability would be at least 0.29 (29%) for a post-treatment measure for analyses. The assumption that 10% of participants with a quantifiable SCA at screening will have SCA below the limit of detection at a pre-treatment

measure is an estimate based on data from A5244 in which 6 of 50 (12%) enrolled participants had undetectable SCA at pre-entry and 5 of 51 (10%) at entry after having a screening SCA  $\geq 1$  copy [65].

For additional secondary endpoints, most endpoints are defined as change in a quantitative measure from baseline to post-infusion (e.g., change from baseline to week 13 in HIV-1 RNA by SCA). Assuming two-sided 0.05 significance, 5000 empirical simulations from a normal distribution with mean change equal to 1 standard deviation with n=12 evaluable participants achieved 85% power to detect a statistically significant change from baseline to post-infusion using an exact Wilcoxon signed-rank test (paired data). Thus, with n=12 there is reasonable power to detect a mean change of 1 standard deviation (SD) or larger. Observed virologic measurements may not be normally distributed or may be partially censored due to assay limits of quantification, and thus, an exact Wilcoxon signed-rank test will be used. Potential immune correlates of antiviral impact will be assessed via exact, non-parametric Spearman rank correlation based methods.

Descriptive statistics and graphical data displays will be used to summarize in vivo measurements of HIV-specific T-cells over the pre- to post-infusion period to assess the pattern and magnitudes of T-cell expansion and persistence for each virus. Measurements of immunity will be evaluated by descriptive statistics at each time point and analyzed by exact, nonparametric methods for paired data to compare changes from pre- to post-infusion. HIV-1 specific immune responses using standard immunoassays and measures of HIV-1 persistence will be analyzed similarly.

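### The 80% power in 10.7.1 for the IUPM sign test fits a rule of at least 11 of 12 decreases, but the test as named rejects at 10 of 12 (two-sided 0.05 assumed)

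*Combined protocol and SAP*

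**What the plan says.** Section 10.6 plans a "non-parametric 2-sided sign test to determine whether or not a significant decrease of IUPM is observed". Section 10.7.1 repeats the test and adds the Wilcoxon signed rank test if no values are censored by the assay. It then states: "With 12 participants there is 80% power to reject" H0 if "the true probability of observing a decrease in IUPM in a participant after VOR/HXTC is 0.93". H0 is given only in words, as "change expected with ART alone", and the alternative as a larger change than that.

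Neither 10.6 nor 10.7.1 gives a significance level, a numerical null probability or a rejection rule for this test. The only level printed in section 10 is in 10.7.2, for the additional secondary endpoints: "Assuming two-sided 0.05 significance". The one statement in 10.7.1 about stable ART, "this magnitude change is rarely seen in participants on stable ART", concerns decreases of more than 6-fold. It does not give the chance of any decrease at all.

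**The concern.** A plain sign test compares the probability of a decrease with 0.5. An analyst who runs the named test at the conventional two-sided 0.05 gets a rejection rule under which power at 0.93 is well above 80%. The printed figure therefore seems to belong to a stricter test than the one described.

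What is at stake is the decision rule for an endpoint that 10.2.1 lists as primary. If exactly 10 of 12 participants show a decrease, the default test calls the result significant and the test implied by the power figure does not. In a single-arm pre/post study this should be settled before the data are seen.

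**Working it through.** **Inputs.** n = 12, 2-sided sign test, P(decrease) = 0.93 and stated power 80% are from 10.7.1. A null of 0.5 is the sign test's usual null and is assumed. Two-sided 0.05 is also assumed, since 10.7.2 prints it for other endpoints only. X, the number of participants with a decrease, is Binomial(12, p). The two-sided p-value is twice the upper tail.

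**1. Reproduce the plan's figure at p = 0.93.**
- P(X = 12) = 0.93^12 = 0.4186
- P(X = 11) = 12 × 0.93^11 × 0.07 = 0.3781
- P(X = 10) = 66 × 0.93^10 × 0.07^2 = 0.1565

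| Reject if | Power at 0.93 | Two-sided level at null 0.5 | P(decrease) for 80% power |
|---|---|---|---|
| X ≥ 9 | 99.2% | 0.146 | 0.802 |
| X ≥ 10 | 95.3% | 79/4096 × 2 = 0.0386 | 0.869 |
| X ≥ 11 | 79.7% | 13/4096 × 2 = 0.00635 | 0.931 |
| X = 12 | 41.9% | 1/4096 × 2 = 0.0005 | 0.982 |

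Only X ≥ 11 gives the stated 80%, and it also gives the stated 0.93.

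**2. The rule of the named test.** At null 0.5 and two-sided 0.05, X ≥ 10 qualifies (0.0386) and X ≥ 9 does not (0.146). The rule is 10 of 12, with 95.3% power at 0.93 and 80% power at 0.869.

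**3. Other routes to 80%.** Normal approximations at null 0.5 and two-sided 0.05 give 97.7% (score), 92.4% (continuity-corrected) and 84.6% (null variance). One tie dropped leaves n = 11, where the rule is 10 of 11 (two-sided level 0.0117) with 82.3% power. With n = 10 it is 9 of 10, with 84.8%. None of these gives 80%.

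**4. Inputs that give X ≥ 11.**
- Null above 0.5, at 0.025 per tail: P(X ≥ 10 | p0) = 0.025 at p0 = 0.5159, and P(X ≥ 11 | p0) = 0.025 at p0 = 0.6152. The null must lie between about 0.516 and 0.615.
- Null 0.5 with a stricter level: two-sided alpha from 0.00635 to just below 0.0386.

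**5. Where the readings part.** Doubled exact p-values:

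| Null | 10 of 12 | 11 of 12 |
|---|---|---|
| 0.50 | 0.039 | 0.006 |
| 0.55 | 0.084 | 0.017 |
| 0.60 | 0.167 | 0.039 |

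Exactly 10 of 12 has probability 16% at p = 0.93 (0.1565 above) and 28% at p = 0.87 (66 × 0.87^10 × 0.13^2 = 0.277).

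**The case against.** The best defence is that nothing printed is contradicted. The 80% can be reproduced, and the mismatch appears only once a reader supplies a null and a level that the plan does not give for this test. The wording of H0 refers to the change on ART alone, not to no change, so a null somewhat above 0.5 may well be intended, and a modest shift to about 0.52 is enough to restore the printed power. The rules differ at one outcome only. The plan will also report the number and proportion with a decrease, the median fold-change with its interval and the proportion above 6-fold, so a reader could judge a result of 10 of 12 without the test.

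Much of this stands, and it rules out two stronger readings. A reader might infer that the power figure is an arithmetic error. The documents do not show that, because unstated inputs reproduce it. A reader might also infer that the study is underpowered. The default reading gives more power than claimed, and 10.3 justifies n = 12 by confidence intervals for adverse events.

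What does not stand is that this is only missing detail. Filling the gap with the named test at the usual level makes the stated power wrong. Keeping the stated power needs either a null that a plain sign test does not use or a stricter level that the plan does not announce. The text gives no probability of a decrease on ART alone from which the first could be derived.

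**Conclusion.** The test named in 10.7.1 and the power printed for it do not match unless an unstated input applies. At null 0.5 and two-sided 0.05, both assumed, power at 0.93 is 95% where the plan says 80%, and 80% power is reached at about 0.87 where the plan says 0.93. The printed figure requires rejection at 11 of 12 or more. That follows from an ART-alone null of about 0.52 to 0.615 at 0.025 per tail, or from a two-sided level of about 0.0063 to below 0.0386 at null 0.5. The practical consequence is limited to a result of 10 of 12, where the conclusion changes with the reading. The exact binomial figures assume no ties. The sample size is not called into question.

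**What to change.** Make the test and the figure agree in 10.7.1.

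- If the null is 0.5 at two-sided 0.05: reword H0 as no change, and state 80% power at a probability of decrease of 0.87 (95% at 0.93). Give the rule as at least 10 of 12 decreases without ties, or at least 10 of 11 if one tie is dropped.
- If H0 is the change on ART alone: state that null probability with its source, and state the alpha. Replace the plain sign test with an exact binomial test against that null. Keep 0.93 only if these inputs give the rule of at least 11 of 12.
- If null 0.5 with a stricter level was intended: print that level. The sign test and 0.93 can then stay, with H0 reworded as no change.

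The cost is a sentence or two in 10.7.1, with no change to sample size or design. The choice should be made before the IUPM results are examined.

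### For in vivo exposure, the pool-level rank-sum test cannot attribute a participant's RNA increase to VOR, because it makes no allowance for variation between collections

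*Combined protocol and SAP*

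**What the plan says.** The protocol's Section 10.7.1 (Primary Analysis) contains two RNA analyses for the first six participants.

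The first is within the participant. The plan states that "we will assess within-participant RNA changes" and continues: "We will analyze using the non-parametric 2-sided Wilcoxon rank sum test". Its stated purpose is to decide whether RNA expression rose significantly. The observations are the individual pools: the test is made by "comparing RNA levels measured in each of 24-36 replicate pools of 1 million resting CD4+ cells". Two exposures are covered: "ex vivo exposure to VOR in the screening step; in vivo exposure to first VOR dose". Undetectable pools are handled by rule: "Pools with undetectable RNA will be considered as 0 copies and analyzed as the lowest rank in this rank-based statistical test". No allowance is made for collection, day or assay run. The text does not say how many collections supply the pools, whether 24-36 is per condition or in total, or what significance level applies.

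The second takes the participant as the unit. The pre-VOR value is "the median RNA copies over the individual pools of one million participant cells tested prior to VOR", and the post-VOR value is formed the same way. Then: "Changes in RNA expression will be evaluated by the sign test and the proportion of participants with increases versus decreases".

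The section describes the RNA measurement as having served "as a gateway to advance through the study protocol". In the current version, however, Section 8.1.1.3 lists a single advancement point, from Step 1 to Step 3, and it depends on IUPM alone.

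**The concern.** Pools made from one collection are replicates of that collection. Their spread shows cell sampling and assay noise. It does not show how RNA per million resting cells would differ between two occasions if no VOR were given, through biology, cell isolation or processing batch. The rank-sum test takes its standard error from the spread among pools alone.

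In the in vivo comparison, the two sets of pools are necessarily separated in time. If occasions differ at all, a small p-value shows that the two sets of cells differ, but not why. Using more pools estimates each collection's level more precisely and adds nothing on how collections vary.

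The same section takes more care with IUPM. There an individual change counts only if it exceeds six-fold, a size chosen because it is uncommon under stable ART. RNA has no such yardstick. What is at stake is whether the report can say that a given participant had a significant RNA response to the first VOR dose.

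**Working it through.** **Inputs.** From Section 10.7.1: unpaired two-sided rank-sum test, pools as observations, 24-36 pools, six participants. Assumed, because the plan does not state them:
- 24-36 is the number of pools per condition (m).
- The two-sided level is 0.05, as Section 10.7.2 states for the additional secondary endpoints.
- Each condition is one collection.
- A share ρ of the total variance lies between collections. The documents give no value, so a range is shown.

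The plan gives no error rate or power for this test, so there is no figure of its own to reproduce.

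**Formula.** With total variance 1, the difference between two collection means has variance 2[ρ + (1−ρ)/m]. The test allows only for 2(1−ρ)/m. The ratio is 1 + mρ/(1−ρ). The approximate null rejection rate is therefore 2Φ(−1.96/√[1 + mρ/(1−ρ)]).
- m = 24, ρ = 0.05: ratio 1 + 24×0.05/0.95 = 2.263, square root 1.504, rate 2Φ(−1.303) = 0.193.
- m = 36, ρ = 0.10: ratio 1 + 36×0.10/0.90 = 5, square root 2.236, rate 2Φ(−0.877) = 0.381.

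**Simulation.** 4,000 comparisons per setting with no VOR effect, normal pool values and a normal collection effect. The Monte Carlo standard error is at most √(0.25/4000) = 0.008.

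| Share ρ | Two-sided rejection, m = 24 / 30 / 36 | False increases, m = 24 / 30 / 36 |
|---|---|---|
| 0 | 0.051 / 0.040 / 0.049 | 0.023 / 0.018 / 0.024 |
| 0.01 | 0.081 / 0.084 / 0.088 | 0.042 / 0.045 / 0.047 |
| 0.05 | 0.173 / 0.202 / 0.246 | 0.091 / 0.107 / 0.121 |
| 0.10 | 0.284 / 0.325 / 0.374 | 0.134 / 0.162 / 0.188 |
| 0.20 | 0.455 / 0.479 / 0.522 | 0.214 / 0.234 / 0.248 |

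The formula and the simulation agree closely. With half the pools undetectable and tied at zero (m = 30), the rejection rates are 0.046, 0.188, 0.294 and 0.446 at ρ = 0, 0.05, 0.10 and 0.20, so the plan's rule for undetectable pools does not remove the inflation.

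**If 24-36 is the total over both conditions,** m is 12-18. At ρ = 0.05 the ratio is 1.632 to 1.947 and the approximate rate 0.12 to 0.16. At ρ = 0.10 the ratio is 2.333 to 3 and the rate 0.20 to 0.26. The inflation is smaller but still present.

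**Across six participants,** with one independent in vivo comparison each and r the two-sided rejection rate, the chance of at least one false increase is 1 − (1 − r/2)^6. For m = 24 and 36 this is about 0.14 at ρ = 0, 0.42 and 0.55 at ρ = 0.05, and 0.60 and 0.71 at ρ = 0.10.

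**Participant as the unit.** Exact two-sided sign test, n = 6: six of six increases gives 2×(1/64) = 0.031; five of six gives 2×(6+1)/64 = 0.219. Only a unanimous result is significant at 0.05.

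**The case against.** The strongest reply is that the plan already contains the sound analysis. Directly after the rank-sum test it reduces each participant to a pre and a post median and applies a sign test to the same six people. That analysis does not have this fault. It stands, and a reader who inferred that the plan's whole RNA inference is invalid would be wrong. It does not, however, repair the separate significance call made for each participant.

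Other limits also stand:
- **Advancement.** The gateway wording might suggest that false positives would move participants forward. The current text does not support that: Step 2 has been removed since Version 3.0, and IUPM is the only advancement criterion. RNA expression is also not listed among the endpoints in Section 10.2.
- **Number of collections.** It is tempting to say that each participant supplies exactly one collection before and one after VOR. The documents do not say so. Section 8.1.1.18 lists two leukaphereses, at baseline and Visit 23, and neither is described as the sample taken after the first dose. The point needs only that the in vivo pools come from different time points and that the test has no collection term.
- **Ex vivo exposure.** If exposed and unexposed pools are split from one collection, this between-collection fault does not arise.
- **Size.** A reader might take the two-sided rejection rates as rates of false increase. Only about half are. Both depend on an assumed variance share, and more pools worsen the error only when that share is above zero.

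It can also be said that the plan speaks of an observed increase and does not itself attribute it to VOR. That is fair, but a significance call on RNA before and after the first dose invites that attribution.

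**Conclusion.** The concern holds for the in vivo, per-participant comparison only. A significant rank-sum result there cannot distinguish a VOR effect from ordinary variation between collections. With 24-36 pools per condition and an assumed 5% or 10% of variance between collections, the two-sided null rejection rate is about 17-25% or 28-37%, and the rate of false increases about 9-12% or 13-19%. If that share is zero, the test holds its nominal level; the documents neither give the share nor offer a way to estimate it.

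Severity is minor. The consequence is confined to how results for the first six participants are reported. No advancement decision or listed endpoint rests on this test.

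**What to change.** In Section 10.7.1, say that for in vivo exposure the per-participant pool distributions and rank-sum p-values are descriptive and will not be reported as a significant increase. Rest any statement about VOR on the sign test of participant medians already in that section. State how many collections supply the pools, whether 24-36 is per condition, and the significance level. The rank-sum test can stay for ex vivo exposure where both sets of pools come from the same collection, and the text should say whether they do.

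The change takes a few sentences and needs no new data. Its cost is that per-participant significance claims for in vivo RNA are given up, and that with six participants the remaining test reaches 0.05 only if all six increase.
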